### 6.2 DATA SHARING PLANS

#### 6.2.1 Human Data Sharing Plan

##### What data will be shared?

I will share human data generated in this research for future research as follows:

- De-identified data in an NIH-funded or approved public repository.
- De-identified data in BTRIS (automatic for activities in the Clinical Center)
- De-identified or identified data with approved outside collaborators under appropriate agreements.

##### How and where will the data be shared?

Data will be shared through (*check all that apply*):

- An NIH-funded or approved public repository, i.e., [www.clinicaltrials.gov](http://www.clinicaltrials.gov).
- BTRIS (automatic for activities in the Clinical Center)
- Approved outside collaborators under appropriate individual agreements.
- Publication and/or public presentations.

##### When will the data be shared? (*check all that apply*)

- Before publication.
- At the time of publication or shortly thereafter.

#### 6.2.2 Genomic Data Sharing Plan

Unlinked genomic data will be deposited in public genomic databases such as dbGaP in compliance with the NIH Genomic Data Sharing Policy.

### 6.3 RESPONSE CRITERIA

For the purposes of this study, patients should be re-evaluated for response at week 2 and week 6.

#### 6.3.1 Definitions

**Evaluable for toxicity:** All patients will be evaluable for toxicity from the time of their first treatment with topical ruxolitinib.

**Abbreviated Title:** Topical ruxolitinib in cGVHD

**Version Date:** 01/25/2021

**Evaluable for objective response:** Patients who complete 6 weeks of treatment will be evaluable for the primary endpoint of efficacy. Patients who have progression of the skin disease earlier will also be included in the analysis of efficacy.

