**Design:**

- This is a Phase II, placebo-controlled, double-blinded study to determine the safety, tolerability and efficacy of topical ruxolitinib in patients with epidermal cGVHD.
- Participants with at least 2 non-ulcerated sites of epidermal cGVHD will apply topical ruxolitinib 1.5% cream to 1 prespecified site and vehicle cream to the second prespecified site twice a day for 6 weeks.
- Safety will be assessed according to CTCAE v5.0 criteria. Assessments will occur during visits and/or phone follow-up every 2 weeks during treatment.
- Efficacy will be assessed at 6 weeks. The initial surface areas of the 2 target lesions will be measured at baseline, week 2, and week 6 on evaluable patients, with the option for an in-person assessment at week 4. The percent decline in the surface area of the 2 lesions will be determined, and the difference in decline between the 2 lesions will be calculated, expressed consistently as ruxolitinib decline minus placebo decline.
- A skin biopsy and peripheral blood samples will be collected prior to treatment and at week 6 to evaluate the cutaneous immune compartment cellular infiltrate, cytokine profiling, STAT phosphorylation, gene expression profiling, and in situ cGVHD biomarkers.
- Pharmacokinetic studies will be performed at week 2.
- Up to 15 patients will be enrolled to achieve 10 evaluable patients, defined as participants who remain active at the time of the primary endpoint. 10 evaluable patients will provide 80% power to detect whether these paired differences in the changes from baseline are equal to one SD of the difference of the changes (effect size=1.0) using a two-tailed 0.05 significance level paired t-test. In practice, a Wilcoxon signed rank test may be used instead of a t-test if the differences are not consistent with a normal distribution ( $p<0.05$  by a Shapiro-Wilks test).

**Abbreviated Title:** Topical ruxolitinib in cGVHD

**Version Date:** 01/25/2021

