### **3.8 CRITERIA FOR REMOVAL FROM PROTOCOL THERAPY AND OFF STUDY CRITERIA**

#### **3.8.1 Criteria for removal from protocol therapy**

- Completion of 6-week protocol therapy
- Progressive disease in skin or other organ system requiring an increase or change in systemic therapy
- Participant requests to be withdrawn from active therapy
- Unacceptable toxicity as defined in Section 11.1.2
- Investigator discretion
- Pregnancy

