### **4.1 CONCOMITANT CORTICOSTEROID THERAPY**

Participants may remain on systemic corticosteroids during the course of the 6-week study at a stable or tapering dose. If a pulse of corticosteroids is required for cutaneous or other organ cGVHD, the patient will be withdrawn from the study. Topical corticosteroids may not be used for the duration of this study.

**Abbreviated Title:** Topical ruxolitinib in cGVHD

**Version Date:** 01/25/2021

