### 8.2 SAMPLE SIZE DETERMINATION:

The primary objectives are to determine the safety and tolerability as well as the efficacy of topical ruxolitinib 1.5% cream in patients with epidermal cGVHD. Patients who are compliant with protocol requirements through the primary endpoint, week 6, are considered evaluable. To analyze the efficacy of the treatment, we will measure surface area percent change. The initial surface area of each of the two target lesions will be measured at baseline and again at week 2, week 4 (optional), and week 6 on evaluable patients after one lesion has received treatment with ruxolitinib 1.5% cream and the other lesion has received treatment with the vehicle control. Following 6 weeks of treatment, the percent decline in the surface area of the two lesions will be determined, and the difference between the two decline percentages between the two lesions will be formed, expressed consistently as ruxolitinib decline minus placebo decline. If there are 10 evaluable patients (complete all study requirements through week 6) who have differences in decline percentages determined, then there will be 80% power to detect whether these paired differences in the changes from baseline are equal to one SD of the difference of the changes (effect size=1.0) using a two-tailed 0.05 significance level paired t-test. In practice, a Wilcoxon signed rank test may be used instead of a t-test if the differences are not consistent with a normal distribution ( $p<0.05$  by a Shapiro-Wilks test).

The anticipated accrual rate is 1 patient per month. Enrollment is open to individuals at least 12 years of age, regardless of gender or racial/ethnic background. Given the complexity of this disease, which is often multiorgan in nature with intermittent flares of disease, the drop-out rate is expected to be high. In order to allow for a modest percentage of patients who are not able to comply with the proper administration of the two agents, the accrual ceiling will be set at 15 patients. Therefore, it is anticipated that the study will last approximately 17 months to reach 10 evaluable patients.

**Abbreviated Title:** Topical ruxolitinib in cGVHD

**Version Date:** 01/25/2021

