### **8.3 POPULATIONS FOR ANALYSIS**

Per protocol analysis dataset: patients who receive at least 80% of scheduled doses of the agent in order to measure the change from baseline to 6 weeks will be included in the statistical analyses performed.

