#### **8.4.2 Analysis of the primary efficacy endpoints**

To analyze the efficacy of the treatment, the initial surface area of each of the two target lesions will be measured at baseline and again at week 2, week 4 (optional), and week 6 on evaluable patients after one lesion received treatment with ruxolitinib 1.5% cream and the other lesion received treatment with the vehicle control. Following 6 weeks of treatment, the percent decline in the surface area of the two lesions will be determined, and the difference between the two decline percentages between the two lesions will be formed, expressed consistently as ruxolitinib decline minus placebo decline. The magnitude of the paired differences will be calculated and tested for whether the difference is equal to zero by a two-tailed 0.05 significance level paired t-test. In practice, a Wilcoxon signed rank test may be used instead of a t-test if the differences are not consistent with a normal distribution (p<0.05 by a Shapiro-Wilks test).

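### Section 6.3.1 includes early skin progressors in the efficacy analysis, but 8.2, applied through 8.4.2, excludes those whose progression ends treatment before week 6

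*Combined protocol and SAP*

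**What the plan says.** Section 6.3.1 makes patients who finish six weeks of treatment evaluable for the primary efficacy endpoint. It then adds: "Patients who have progression of the skin disease earlier will also be included in the analysis of efficacy".

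Four other places define who counts:

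- **Section 8.2** bases its power on "10 evaluable patients (complete all study requirements through week 6", and also asks for compliance with the protocol up to that point.
- **Section 8.4.2** takes its measurements on evaluable patients and continues: "Following 6 weeks of treatment, the percent decline in the surface area of the two lesions will be determined".
- **Section 8.3** names one dataset, per protocol, made up of "patients who receive at least 80% of scheduled doses of the agent".
- **The précis (Design)** has evaluable patients "defined as participants who remain active at the time of the primary endpoint". It does not say whether active means on treatment or on study.

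Three sections govern what happens at progression. Section 3.8.1 ends protocol therapy for "Progressive disease in skin or other organ system requiring an increase or change in systemic therapy". Section 4.1 goes further: "If a pulse of corticosteroids is required for cutaneous or other organ cGVHD, the patient will be withdrawn from the study". Section 3.8.2 lists only completed follow-up, participant request and death as reasons to leave the study.

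Section 3.1 plans an in-person week 6 visit with surface-area measurement for all participants, not only for those still on cream.

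**The concern.** The sentence in 6.3.1 adds something only for patients who do not finish six weeks, since completers are already covered. Those are the patients 8.2 leaves out. The analyst would have two written definitions of the primary efficacy set and no rule of precedence.

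If section 8 is followed, pairs are lost because the skin got worse, which is the outcome under study. Section 8.2 gives reason to expect this: it describes a disease "with intermittent flares of disease, the drop-out rate is expected to be high". With 10 pairs, each carries a tenth of the mean, and 6.3.4 hopes to use the result to set response criteria for a larger trial. If the choice between definitions were made after unblinding, it would be open to challenge whichever way it went.

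**Working it through.** **1. The plan's own power.** Inputs from 8.2: 10 pairs, effect 1.0 SD of the paired difference, two-sided 0.05 paired t-test. The noncentral t with 9 degrees of freedom and noncentrality 1.0 × √10 = 3.16 gives 80.3%. The stated 80% reproduces and is not in dispute.

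**2. Who is in and who is out.** The dose rule in 8.3 needs a count. Section 3.2 gives twice-daily application for 6 weeks: 2 × 7 × 6 = 84 doses per site. Then 0.80 × 84 = 67.2, so 68 doses, or 34 full days.

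| Patient | 6.3.1 | 8.2 and 8.4.2 | 8.3 |
|---|---|---|---|
| Skin progression, no systemic change, finishes week 6 | in | in | in, if at least 68 doses |
| Skin progression ends therapy before day 34 | in | out | out |
| Skin progression ends therapy from day 34 to before week 6, no missed dose | in | out | in |
| Stopped only for another organ | not covered by the added sentence | out | by dose count |

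The conflict lies in the second and third rows.

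**3. Is there a value to analyse?** For a patient removed under 3.8.1 without a steroid pulse, yes. Section 3.8.2 does not take the patient off study, and the week 6 visit in 3.1 still applies. For a pulsed patient, the wording of 4.1 removes that visit. No visit is triggered by progression itself.

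**4. What dropping the pairs could do (illustration only).** Assumed, not in the documents: normal data, true difference 1.0 SD, equal site variances, between-site correlation 0.5, and the worst fraction f of pairs lost. If one site drives the loss, the retained mean shifts by 0.5 × φ(z_f)/(1 − f). At f = 0.20 this is 0.5 × 0.280/0.80 = 0.175. Simulated retained means:

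| What drives loss | f = 0.10 | f = 0.20 |
|---|---|---|
| Vehicle site worsening | 0.90 | 0.83 |
| Active site worsening | 1.10 | 1.17 |
| Worse of the two sites | 0.92 | 0.86 |
| Combined decline of both | 1.00 | 1.00 |

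At f = 0.20, with correlation from 0 to 0.8, the vehicle-driven mean runs from 0.75 to 0.89 and the active-driven mean from 1.25 to 1.11.

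**5. What including the pairs could do (also illustration).** Ten completers with mean 1.0 SD, plus progressors with SD 1 and an assumed mean difference:

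| Progressor mean | One added | Two added |
|---|---|---|
| 1.0 SD | 85% | 88% |
| 0.5 SD | 81% | 81% |
| 0 | 75% | 70% |
| −1.0 SD | 56% | 36% |

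At mean 0 the pooled effect is 10/11 = 0.91 SD with one added and 10/12 = 0.83 SD with two. If such progressors were counted within the 10 instead of added, power would be 68% with one and 55% with two.

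**The case against.** Several points on the other side have force.

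- **A reader might infer that progressors have no lesion measurement to contribute.** The documents do not support that. Section 3.1 plans the week 6 assessment for everyone, week 2 is mandatory, and 6.3.3 calls for tracing at each visit. Only the pulse wording in 4.1 takes the week 6 value away.
- **A reader might infer that the précis, 8.2 and 8.3 all firmly exclude these patients.** Only 8.2 clearly does. The précis leaves active undefined, and 8.3 is a dose count that a fully adherent patient treated through day 34 passes. Section 8.2 still carries weight because 8.4.2 takes up its term.
- **The phrase in 6.3.1 about the analysis of efficacy might mean secondary scales or patient listings.** This is possible but strained: the sentence follows directly on the primary endpoint and says these patients are also included.
- **Progression that needs a systemic change plausibly affects both sites.** Then the retained mean may not move at all, as the last row of the bias table shows. This stands.
- **Deleting the sentence in 6.3.1 would also end the contradiction, and including progressors may cost power.** Both are true. Deletion, however, gives up the plan's own inclusion rule and settles on outcome-related loss. For a pilot either rule could be defended if it were stated; at present both are written.

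**Conclusion.** The contradiction is certain. It is confined to patients whose skin progression ends therapy before week 6, and it decides who enters the primary test. It is a conflict between definitions, not an arithmetic error.

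Its practical size is not known. The ceiling of 15 for 10 evaluable patients allows up to 5 of 15 (33%) to be non-evaluable, but nothing says how many would be skin progressors. A reader might infer that the estimate will be biased in favour of ruxolitinib or against it. The documents support neither: the direction depends on which site drives removal, and there may be no bias. The bias and power tables rest on assumed correlations, loss fractions and progressor effects, and show only that a few pairs can matter at this sample size. The plan should be corrected, and the correction is cheap.

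**What to change.** 1. Amend the précis, 8.2, 8.3 and 8.4.2 so that patients removed early for skin progression enter the primary paired analysis, as 6.3.1 says. Keep the 80%-dose completer set as a sensitivity analysis.
2. In 4.1, replace withdrawal from the study with removal from protocol therapy per 3.8.1, and keep the patient on study so that the week 6 visit takes place.
3. State before unblinding which value such a pair contributes: the planned week 6 measurement or, if there is none, the last on-study measurement of both sites, taken at the progression visit and before the pulse where such a visit occurs. Use the alternative value in a sensitivity analysis. Call a pair missing only if no post-baseline measurement exists.
4. State that the 80% power refers to 10 week 6 completers, with progressors added to them and not counted toward them.

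The cost is wording plus, where a progression visit occurs, one extra lesion measurement; the ceiling of 15 can stay. There are three downsides. Week 6 values may reflect new systemic therapy, though both sites share that exposure. Earlier values mix time points within one test. Power drops below 80% if the added progressors show little between-site difference.

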### 6.3.2 Disease Parameters

**Measurable disease:** Measurable lesions are defined as areas that are clinically consistent with epidermal cGVHD that are at least 8cm (or approximately 1 palm size for children) in shortest diameter.

**Target lesions.** Two areas of measurable disease that are on separate body regions (e.g. right arm and left arm) at least 10 cm apart, amenable to topical application of medicine will be identified as **target lesions** and recorded and measured at baseline. Target lesions should be selected on the basis of their size (lesions with the longest diameter), and be representative of the morphology of epidermal cGVHD present in the patient, be nonulcerated, show no evidence of cutaneous infection, show no evidence of current or prior NMSC, and in addition should be sites that lend themselves to reproducible repeated measurements.

### 6.3.3 Methods for Evaluation of Measurable Disease

All measurements will be taken and recorded in metric notation using a ruler or calipers. All baseline evaluations should be performed as closely as possible to the beginning of treatment and never more than 1 week before the beginning of the treatment.

The same method of assessment and the same technique should be used to characterize each identified and reported lesion at baseline and during follow-up.

**Clinical examination:** Clinical photographs, photographs for automated measurements, and transparency tracing will be used at each visit for accurate measurements of the target areas of affected skin. Surface area of each target lesion will be calculated. An overall Physicians Global Assessment score will be documented at each visit.

### 6.3.4 Response Criteria

#### 6.3.4.1 Evaluation of Target Lesions

No definition of response exists for epidermal cGVHD. The 2014 Response Criteria Working Group of the NIH Consensus Development Project on Criteria for Clinical Trials in Chronic Graft-versus-Host Disease recommended a scoring system (0-3) for cutaneous GVHD that takes into account total BSA for cutaneous cGVHD findings, depth of sclerotic cGVHD, and presence of ulceration.(20) This scoring system cannot be used for our purposes, as such there is no validated or defined scale and response criteria for epidermal cGVHD.

This pilot study will evaluate the percent decline surface area after 6 weeks of treatment with topical ruxolitinib cream and vehicle cream to define a clinically relevant difference. This will potentially define a response criteria to be used for a subsequent, larger trial of topical ruxolitinib for epidermal cGVHD.

*Abbreviated Title:* Topical ruxolitinib in cGVHD

*Version Date:* 01/25/2021

#### **6.4 TOXICITY CRITERIA**

The following adverse event management guidelines are intended to ensure the safety of each patient while on the study. The descriptions and grading scales found in the revised NCI Common Terminology Criteria for Adverse Events (CTCAE) version 5.0 will be utilized for AE reporting. All appropriate treatment areas should have access to a copy of the CTCAE version 5.0. A copy of the CTCAE version 5.0 can be downloaded from the CTEP web site ([https://ctep.cancer.gov/protocolDevelopment/electronic\\_applications/docs/CTCAE\\_v5\\_Quick\\_Reference\\_5x7.pdf](https://ctep.cancer.gov/protocolDevelopment/electronic_applications/docs/CTCAE_v5_Quick_Reference_5x7.pdf)).

### **7 SAFETY REPORTING REQUIREMENTS/DATA AND SAFETY MONITORING PLAN**

#### **7.1 DEFINITIONS**

Please refer the Policy 801 for definitions of reportable events.

#### **7.2 EXPEDITED REPORTING TO NIH INTRAMURAL IRB**

Please refer to the Policy 801 for expedited reporting requirements.

#### **7.3 NIH INTRAMURAL IRB REQUIREMENTS FOR PI REPORTING AT CONTINUING REVIEW**

Please refer to the reporting requirements in Policy 801

#### **7.4 NIAMS CLINICAL DIRECTOR REPORTING**

All serious adverse events (SAEs) that meet the definition per Policy 801, must be reported to NIAMS Clinical Director via [[contact]](mailto:[contact])

#### **7.5 IND SPONSOR REPORTING CRITERIA**

An investigator must immediately report to the sponsor, using the mandatory MedWatch form 3500a or equivalent, any serious adverse event, whether or not considered drug related, including those listed in the protocol or investigator brochure and must include an assessment of whether there is a reasonable possibility that the drug caused the event.

- All Grade 5 (fatal) events (except death due to progressive disease) must be reported via email within 24 hours. A complete report must be submitted within one business day.
- All other serious adverse events including deaths due to progressive disease must be reported within one business day

Study endpoints that are serious adverse events (e.g. all-cause mortality) must be reported in accordance with the protocol unless there is evidence suggesting a causal relationship between the drug and the event (e.g. death from anaphylaxis). In that case, the investigator must immediately report the death to the sponsor.

Events will be submitted to PI and study coordinator.

Events will be submitted to [REDACTED], authorized representative for the IND Sponsor (NIAMS) at:

**Abbreviated Title:** Topical ruxolitinib in cGVHD

**Version Date:** 01/25/2021

### 7.5.1 Reporting Pregnancy

#### 7.5.1.1 Maternal exposure

If a patient becomes pregnant during the course of the study, the study treatment should be discontinued immediately and the pregnancy reported to the Sponsor. The potential risk of exposure of the fetus to the investigational agent(s) or chemotherapy agents (s) should be documented in box B5 of the MedWatch form "Describe Event or Problem".

Pregnancy itself is not regarded as an AE unless there is a suspicion that the study treatment under study may have interfered with the effectiveness of a contraceptive medication. However, as patients who become pregnant on study risk intrauterine exposure of the fetus to agents which may be teratogenic, the CCR is requesting that pregnancy should be reported in an expedited manner as **Grade 3 "Pregnancy, puerperium and perinatal conditions - Other (pregnancy)"** under the **Pregnancy, puerperium and perinatal conditions** SOC.

Congenital abnormalities or birth defects and spontaneous miscarriages should be reported and handled as SAEs. Elective abortions without complications should not be handled as AEs. The outcome of all pregnancies (spontaneous miscarriage, elective termination, ectopic pregnancy, normal birth, or congenital abnormality) should be followed up and documented.

If any pregnancy occurs in the course of the study, then the investigator should inform the Sponsor within 1 day, i.e., immediately, but **no later than 24 hours** of when he or she becomes aware of it.

The designated Sponsor representative will work with the investigator to ensure that all relevant information is provided to the Sponsor within 1 to 5 calendar days for SAEs and within 30 days for all other pregnancies.

The same timelines apply when outcome information is available.

